Informed consent for DTM will include a detailed description, in English and Spanish, of the risks and benefits of the study with user-friendly images of the equipment. If the patients decline to participate in DTM, they will continue to receive standard of care and still have surveys administered and data collected over time (as agreed to in consent 1). Based on intention to treat (ITT), they nevertheless will be analyzed as part of the DTM group.

For those patients randomized to DTM, the RN will explain to the patients that if they agree to participate, they will be asked to measure vital signs daily, receive weekly telehealth “visits” with the telehealth RN (with appropriate assurances regarding confidentiality), and receive reminders of their weekly visits. The experienced bilingual RN will be trained in the proper recruitment of patients to eliminate selection bias based on a standardized protocol. The research RN will also explain to the DTM patient that s/he will have a bilingual trainer meet them at their home and that they will receive training on how to properly use the equipment.

For those patients randomized to COM, the research RN will have monthly phone contacts to determine how the patient is doing, how many days during the week they have been sick, and whether they have been to an unscheduled doctors visit, the ED or hospital during the last month and how many days they have been sick. Lastly, in both groups, the enroller will let patients know that they will be asked to complete pre and post surveys. The enroller will be trained on the proposed enrollment practices to ensure objective, unbiased and systematic selection and recruitment of participants.

DTM patients will be asked if they prefer to involve their caregiver; if patients agree, caregivers will be provided with the caregiver app (Figure 3). The bilingual enroller will explain to DTM patients that they will provide DTM training at their home.

We propose to study H/L patients with T2D, recruited from the Ambulatory Care Unit at LIJMC and the Division of General Internal Medicine Practice located in Queens NY, one of the most diverse populations in the world. We also propose to recruit at Southside Hospital. NUMC and Glen Cove Hospital as well as the Dolan Family Health Center. We selected these sites because 1) clinic patient statistics meet our enrollment criteria, with 4,092 adults H/L patients with T2D (well over the

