**Comparator: Comprehensive Outpatient Management (COM)** is the most realistic evidence-based comparator, in that it is the most frequently recommended and used option for US T2D patients. COM, like DTM, is consistent with the 2018 ADA Standards which include, but are not limited to, past medical and family history, social history, medications, screening, physical examination, laboratory evaluation, etc. We will measure adherence to these standards using a chart review checklist to assess issues of fidelity and differential adherence. Patients are instructed to monitor BG (within physician recommendations) BG monitoring will individualized throughout the study. Frequency of BG monitoring will vary depending on medication, A1c readings, sick days and stress levels, and have routine or “well” visits every 3 months. Patients can set appointments with a T2D educator. COM patients will receive monthly calls from the study RN to collect data. In the “real world,” COM patients would not receive such calls; however, to maximize retention, this will favor our outcomes *toward the null hypothesis*, thereby increasing our confidence in intervention effects of DTM relative to COM. **Formal Study Protocol.** We have initiated formal protocol development. It will include our research objectives, design, outcomes, and detailed analytical methods. We will provide internationally standardized data dictionaries, final study protocol documents, data sheets, study population descriptions, covariates used in analyses, discussion guides and qualitative research coding information and any other original materials that facilitate study replication along with the first 12-month progress report, and within 3 months of the end of the funding period. We understand that PCORI reserves the right to share our materials with other researchers. If funded, our work will be available for evidence synthesis, at <http://www.crd.york.ac.uk/prospero/> and our clinical trial will be registered at [www.clinicaltrials.gov](http://www.clinicaltrials.gov). **Stakeholder Engagement.** Consistent with PCORI’s engagement rubric, **there are five ways in which patient/stakeholder input has been and will continue to be critical (See Figure 5: Stakeholder Engagement) 1. Community Advisory Board** will ensure that DTM and outcomes have relevance for patients and provide the study team with stakeholder perspectives, tailoring, implementation, and evaluating DTM. The CAB will lead the discussion on study outcomes, adaptation, usability, program satisfaction, and dissemination, and will review and approve the study protocol and resolve issues to ensure project success. For example, the CAB of our previous PCORI study identified a barrier (“fear of undocumented patient identification via weekly video visits”) and strongly recommended that the study team develop appropriate enrollment process protocols. We will use a similar strategy for this current proposal. Engagement will depend on the issue at hand; stakeholders bring different skills to the CAB (e.g., community dissemination of study results may be led by our H/L CBO representative, as she has expertise in this area, particularly with NY H/L media). **See Research Team and Environment for details on CAB stakeholders and their expertise.** Stakeholders bring different skills to the CAB (e.g., community dissemination of study results may be led by our community representatives and legislators, as they have expertise in this

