**1b. Quantitative approach.** This adaptation phase involves an ongoing formative process evaluation of usability using quantitative methods so that adjustments can be made as DTM is implemented. Below is how we will operationalize usability measures. **The first two usability variables will be collected upon subject enrollment in the RCT:**

**1bi. Rate of acceptability.** To simulate the rate of DTM acceptability in the real outpatient environment, we propose to determine, among those who DO NOT consent to be part of the study, the proportion who state that their reason is related to the technology (as opposed to those who simply do not want to be part of a study). This will allow us to compute the “acceptability rate” (as opposed to “acceptance rate” below). Data from other studies most similar to the intervention proposed herein indicate that telehealth acceptability in a general population may be as high as 96%. As acceptability may be different for the H/L disparity population, it is important to measure. Assuming the probability of acceptability in disparity populations is significantly lower (50% rather than 96%) and a total of 200 (240, assuming a 10% attrition rate) patients will need to be randomized (100 per arm) then, approximately 400 patients will need to be approached to yield 200 who consent to enroll. The actual acceptability rate will be calculated as  $X/200$ . Assuming the rate=50% and  $n=200$ , acceptability rate can be estimated to within +/- 7.1% using (95% CI for proportions).

**1bii. Rate of equipment acceptance:** Of those randomized to DTM, the rate of “acceptance” will be the % of patients who accept the app and peripherals. We will randomize 200 patients (240, assuming a 10% attrition rate), to yield a maximum of 100 patients per arm/3 years, the maximum number that can be treated with DTM over 6 months. Assuming 90% of DTM patients will constitute the usability sample, DTM acceptance is estimated +/- 6% (95% CI for proportions). ITT analysis will include all patients randomized to DTM. **The following usability variables will be collected during and upon completion of RCT:**

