**diabetes QoL, GM, BP, cholesterol, medication adherence, and diabetes SE, and reduced diabetes distress, PAID, inpatient utilization, unscheduled T2D physician visits and sick days.**

**Primary Analysis for Aim 2.** Our primary outcome, the basis of our sample size calculation, is change in HbA1c for DTM relative to COM from **baseline to 180 days**. We will use the modified Zelen RCF method. For this continuous data, we will use mixed models repeated measures analysis of covariance (ANCOVA) (SAS 9.4; SAS Institute, Cary, NC) to compare the change in pre-post DTM HbA1c with the change in pre-post COM HbA1c, adjusting for caregiver status (Y,N). In keeping with ICH E9 statistical principles for clinical trials (V.7G) with a stratification variable, the interaction term for treatment x caregiver status will be included in the primary analysis, as well as main effects for treatment and caregiver status. Upon finding a significant treatment x caregiver interaction, treatment effects will be estimated separately for those with and without a caregiver (using ANCOVA for unequal slopes).

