**SECTION FIVE: SAMPLE SIZE JUSTIFICATION**

Our estimated sample size is 224 patients (240, assuming a 10% attrition rate): 112/group, yielding 80% power to detect a 0.5% difference in the pre-post change in HbA1c (two-tailed t-test with  $\alpha = .05$ ) over 6 months. Our power calculation is based on Polisena et al.'s meta-analysis. We computed a sample size-weighted median of the 12 standard deviations (SD) for HbA1c, yielding a value of 1.2%. If the SD of the pre-post 6-month change in HbA1c is 1.2% in each group, a 0.45% difference in this 6-month change yields a 0.42 effect size (ES). This ES is realistic, falling between 2 sets of reductions in the literature: the Diabetes Control and Complications Trial (1% decline in HbA1c reduced microvascular complications by 30%) and RCTs/meta-analyses citing reductions of 0.3% as "clinically significant". Our reduction of 0.45% falls between those limits, is clinically significant/meaningful, as patients can see improvements in their scores. In a systematic review of 13 RCTs (n=4,207) telehealth was associated with a clinically significant mean HbA1c decline of -0.44% compared to COM. In medically underserved patients, telehealth led to a net improvement in HbA1c, cholesterol, and BP. Although our main power calculation refers to our primary outcome (HbA1c), power is still acceptably high for secondary variables (SE, distress or QoL) such that 112 patients/group will yield 80% power to detect an effect size of 0.4 SDs, using a simple t-test to sample size and power.

Figure 4. Study Plan: Following 240 Patients for 12 Months Randomized to Either DTM (n=100) or COM (n=100) with 6 Month Intervention, Assuming 10% Attrition, Resulting in a Final Sample Size of 200

Year	2019												2020												2021												2022																																																	
Month	1	2	3	4	5	6	7	8	9	10	11	12	13	14	15	16	17	18	19	20	21	22	23	24	25	26	27	28	29	30	31	32	33	34	35	36	37	38	39	40	41	42																																												
Enrollment	CAB Focus Group: Confirm Outcomes, Preliminary Intervention Adaptions & Study Design												PAC Focus Group: Confirm Outcomes, Preliminary Intervention & Study Design Adaptions & Recommendations												Provider Focus Group: Pre-Pilot Adaptation Recommendations												CAB: PAC: Provider Focus Group Analysis												Pre-Pilot Adaptation Approval by the CAB																																					

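### Patients who refuse DTM after randomisation stay in the DTM arm, but the sample size does not say whether its target allows for them, and no effect is planned for those who accept

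*Combined protocol and SAP*

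**What the plan says.** - **Timing of the offer.** 6. Recruitment Methods describes a first consent to data collection, then randomisation, then a second consent to DTM for those allocated to it. The primary analysis for Aim 2 (12. Statistical Analysis) names the design: "We will use the modified Zelen RCF method".
- **Refusers.** 6. Recruitment Methods states: "If the patients decline to participate in DTM, they will continue to receive standard of care". Their data are still collected, and "Based on intention to treat (ITT), they nevertheless will be analyzed as part of the DTM group". Item 1bii of 12. Statistical Analysis agrees: "ITT analysis will include all patients randomized to DTM".
- **Expected acceptance.** Item 1bii: "Assuming 90% of DTM patients will constitute the usability sample, DTM acceptance is estimated +/- 6% (95% CI for proportions". The figure is used only for the precision of the acceptance rate.
- **Sample size.** Section Five: Sample Size Justification gives "112/group, yielding 80% power to detect a 0.5% difference in the pre-post change in HbA1c". It then uses an SD of 1.2% and a difference of 0.45%, which it calls an effect size of 0.42. It supports 0.45% by its place between reductions of 0.3% and 1%, and by a pooled telehealth-versus-COM estimate of -0.44%. The only allowance is 10% attrition.
- **Analyses.** The primary, secondary, tertiary and subgroup analyses for Aim 2 contain no estimate of the effect in patients who accept DTM.

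**The concern.** If some patients in the DTM arm never receive DTM, the difference that the ITT comparison can expect is the effect in acceptors multiplied by the acceptance proportion. A sample size has to be read against that product. Here the reader cannot tell whether the target is the product or the undiluted effect. Supporting the target with a telehealth-versus-COM estimate from other trials makes the undiluted reading plausible.

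Two things are at stake. The power for the primary outcome may be lower than stated. And Aim 2 is worded around patients who receive DTM, while the only planned estimate concerns patients who are offered it.

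**Working it through.** **Inputs.** From Section Five: SD of change 1.2% per group, two-sided alpha 0.05, two-sample t-test, 112 per group, difference 0.5% or 0.45%. From 1bii: acceptance 90%. Assumptions made here: refusers have no DTM effect, the SD stays at 1.2%, and all 112 per group are evaluable. The 80% and 95% acceptance values are a range placed around the plan's 90%; the documents do not give them.

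**Step 1: reproduce the plan's figure.** Using n per group = 2 × (1.960 + 0.842)² × SD² / difference²:

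- Difference 0.45%: 2 × 7.85 × 1.44 / 0.2025 = 111.6, so 112.
- Difference 0.5%: 2 × 7.85 × 1.44 / 0.25 = 90.4, so 91.

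Only 0.45% gives 112. With the noncentral t distribution, 112 per group has 79.8% power for 0.45% and 87.4% for 0.5%. The stated effect size of 0.42 belongs to the other figure: 0.5 / 1.2 = 0.417, whereas 0.45 / 1.2 = 0.375.

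**Step 2: confirm that 90% is used as an acceptance rate.** 1.96 × √(0.9 × 0.1 / 100) = 0.059, which matches the ±6% in 1bii.

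**Step 3: dilute.** ITT difference = acceptance × effect in acceptors. Power at 112 per group (noncentral t):

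| Acceptance | ITT difference if 0.45% is the effect in acceptors | Power | ITT difference if 0.5% is the effect in acceptors | Power |
|---|---|---|---|---|
| 100% | 0.450% | 79.8% | 0.500% | 87.4% |
| 95% | 0.4275% | 75.6% | 0.475% | 83.9% |
| 90% | 0.405% | 71.0% | 0.450% | 79.8% |
| 80% | 0.360% | 60.8% | 0.400% | 70.0% |

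Mixing acceptors and refusers in one arm also adds a little variance, but this hardly matters. In the normal approximation, power at 0.405% moves from 71.4% to 71.1%.

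**Step 4: size needed for 80% power, for scale.** By the Step 1 formula, a difference of 0.405% needs 138 per group (2 × 7.85 × 1.44 / 0.164 = 137.8), and 0.40% needs 142 per group.

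**The case against.** Much of the case on the other side stands.

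- **A reader might infer that the 80% power assumes every DTM patient receives the full effect.** The documents do not say so. Section Five powers a between-group difference, the groups are defined elsewhere as ITT groups, and 0.45% is defended partly as clinically meaningful. If 0.45% is the smallest ITT difference worth detecting, nothing is diluted and 112 per group is right.
- **A reader might infer that the design cannot deliver its stated power.** With 0.5% as the effect in acceptors and 90% acceptance, the ITT difference is 0.45% and power is 79.8%. Equally, no passage derives 0.45% as 0.9 × 0.5%, so this agreement does not show that refusal was planned for.
- **A reader might take 50% as the acceptance of DTM.** Item 1bi does say "Assuming the probability of acceptability in disparity populations is significantly lower (50% rather than 96", but it applies the figure to approaching 400 patients so that 200 consent to enrol, and 7. Eligibility Criteria uses 50% in the same way. It is not a Consent 2 rate. The planning value for that step is the 90% in 1bii.
- **The -0.44% may already include non-use.** The documents do not say whether the cited trials had comparable refusal. If they did, multiplying by acceptance would count dilution twice.
- **A null result would not be uninterpretable.** The plan reports equipment acceptance, vital-sign adherence, visit completion and a CONSORT flow, so low uptake would be visible.
- **ITT is a legitimate primary analysis,** and the type I error is unaffected.

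What remains is that the target is undefined and that the effect in acceptors is not estimated. Descriptive uptake figures do not supply that estimate.

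**Conclusion.** The concern holds in conditional form. The documents settle that refusers are analysed in the DTM arm, that the sample size states no allowance for refusal, and that no effect in acceptors is planned. They do not settle which quantity the 0.5% or 0.45% represents.

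If 0.45% is the effect in acceptors, the plan's own acceptance figure costs about 9 points of power (79.8% to 71.0%). If it is 0.5%, power stays at about 80% at 90% acceptance and falls below that if acceptance is lower. If the target is already an ITT difference of 0.45%, there is no loss.

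The figures rest on refusers gaining nothing from the offer and on 112 evaluable patients per arm. Adjustment for baseline HbA1c could recover some power, but the documents give no correlation from which to calculate it.

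**What to change.** 1. Keep ITT as the primary analysis.
2. In Section Five, state one target difference, correct the effect size to match it, and say whether it is the ITT difference or the effect in acceptors.
3. Restate power for the ITT difference (acceptance × effect) at 90% acceptance, with a range such as 80% to 95%. Do not use the 50% enrolment figure for this.
4. Pre-specify one supplementary complier-average effect on the change in HbA1c to 180 days, with randomisation as the instrument. Non-compliance is one-sided because the comparator table lists no telehealth components for COM. In its simplest form the estimate is the ITT difference divided by the acceptance proportion, for example 0.405% / 0.9 = 0.45%. Report it beside ITT with the 1bii acceptance rate, and define acceptance once, as consent to DTM or as taking the equipment.

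**Cost.** This takes some SAP wording and one analysis of data already collected, with no added patients. The complier estimate has a wider interval (roughly 1 / 0.9 = 1.11 times at 90% acceptance), gains essentially no power, and relies on refusers being unaffected by the offer. The restated power may be less favourable; the change makes it clear but does not restore it.

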## 6. RECRUITMENT METHODS

- *Describe the source of potential subjects*
- *Describe the methods that will be used to identify potential subjects*
- *Describe any materials that will be used to recruit subjects. A copy of any advertisements (flyers, radio scripts, etc.) should be submitted along with the protocol.*
- *If monetary compensation is to be offered, this should be indicated in the protocol*

To limit selection bias, and ensure true random selection, our Biostatistics Unit will randomly (using a random number generator) sample 400 patients from the 4,092 total patients.

**Recruitment:** The bilingual study RN, Multisite Patient Engagement Specialist or study coordinator will be responsible for recruitment at the various study sites. Given COVID-19 pandemic we will also be calling be patient over the phone to recruitment.

**Recruitment for Data Collection:** Eligible patients will be approached and called for consent (consent form 1) to have longitudinal data collected, including surveys at specified time points over the 12 months of their participation. Patients who are called will be give verbal consent. Next, bilingual study RN, Multisite Patient Engagement Specialist or study coordinator will obtain the randomization number from the Biostatistics Unit for the patient to determine if they were allocated to the DTM arm or COM arm. If the patient is randomized into the DTM arm, the recruiter will approach to obtain a second consent (consent form 2) to receive DTM. Verbal consent will be given for patients who are called for recruitment.

Informed consent will include a detailed but simple description, in patient's preferred language, of study risks/benefits.

**Recruitment for DTM:** Eligible patients will be approached or called for consent (consent 1) to have longitudinal data collected, including surveys at specified time

points over the 12 months from signing consent, in order to determine health outcomes. Next, the research coordinator will obtain the randomization number for the patient to determine if they were allocated to the DTM arm or COM arm. If the patient is randomized into the DTM arm, the coordinator will approach to obtain a second consent (consent 2) to receive DTM.

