	Pilot												Pilot Patient/Caregiver Focus Groups (2)												Pilot Analysis												PAC Focus Group: Post-Pilot Adaptions												Provider Focus Group: Post-Pilot Adaptions												CAB Finalizes Intervention Adaption												Analysis													
Interventions	CAB												PAC												CAB												Pilot Study												Pilot Focus Groups												PAC												CAB												CAB/BPAC	
	6 MONTH FOLLOW UP												12 MONTH FOLLOW UP												12												12												12												12												12													
Study Aims	Specific Aim 1: Assess usability of an evidence-based DTM intervention utilizing a community based participatory research approach and adapt it to facilitate acceptability and feasibility in a population of Hispanic/Latino patients with T2D, and their caregivers and providers.																																										Specific Aim 2: Assess whether Hispanic/Latino patients receiving DTM attain significantly improved patient-centered outcomes compared to COM, through a CER RCT. Expected outcomes include: improved diabetes quality of life, glycemic management, blood pressure, cholesterol, medication adherence, and diabetes self-efficacy, and reduced diabetes distress, problem areas in diabetes, inpatient utilization, unscheduled T2D physician visits and sick days.																																											

1. Estimated number of potentially eligible participants (describe how number was determined [e.g., Electronic Health Record, claims data, clinic logs, administrative data, other]):	4092
2. Total number of study participants expected to be screened:	400
3. Total number of study participants expected to be eligible of those screened:	400
4. Target sample size (use same number stated in milestones):	200
5. If applicable, total number of practices or centers that will enroll participants:	2
6. Projected month first participant enrolled (month after project initiation):	1/2019
7. Projected month last participant enrolled (month after project initiation):	12/2021
8. Projected rate of enrollment (anticipated number enrolled per month of enrollment period):	8 to 10
9. Estimated percentage of participant dropout:	10%

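### Six or so recruiting sites are named, but the enrolment table counts two centres and neither the described allocation nor the HbA1c model uses site: a modest loss of precision, not a bias

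*Combined protocol and SAP*

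**What the plan says.** **Sites.** Sections 5 and 6 name the Ambulatory Care Unit at LIJMC and a General Internal Medicine practice in Queens, then add: "We also propose to recruit at Southside Hospital. NUMC and Glen Cove Hospital", and finally the Dolan Family Health Center. That is six locations, or five if the two Queens practices count as one. Section 27 separates the Northwell sites from an external site. Row 5 of the enrolment table, in the sample size section, gives 2 for the "total number of practices or centers that will enroll participants".

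**Allocation.** Section 6 says that the recruiter "will obtain the randomization number from the Biostatistics Unit for the patient". No stratification or blocking by site is described.

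**Model.** The primary analysis for Aim 2 (section 12) is a mixed-model repeated-measures ANCOVA of HbA1c change, "adjusting for caregiver status (Y,N"), with the treatment by caregiver interaction. The HTE plan adds gender and its interaction with treatment. Site appears in no primary, secondary, sensitivity or subgroup analysis.

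**Sample size.** The plan states "112/group, yielding 80% power to detect a 0.5% difference in the pre-post change in HbA1c", using a "two-tailed t-test with" alpha of .05.

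**The concern.** Sites can differ in patient mix, staffing and how closely care follows the standards. Section 12 argues that confounding is highly unlikely under randomisation, but it says so about demographics and does not mention site. The comparator section (section 11) itself foresees uneven delivery, since it plans a chart-review checklist covering fidelity and differential adherence.

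If HbA1c change differs by site, that variation stays in the error term of the primary comparison. Without balancing by site, the arms can also differ by chance in their site mix. Each patient's site is recorded without extra effort, so the information would be left unused.

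The centre count matters separately. Two centres and six lead to different decisions on stratification and on pooling small sites, so the plan has to settle the number first.

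**Working it through.** **Inputs.** From the sample size section: 112 per arm, two-sided alpha 0.05, and an SD taken from "If the SD of the pre-post 6-month change in HbA1c is 1.2% in each group". That paragraph gives two target differences, 0.5% in the power sentence and 0.45% further on ("a 0.45% difference in this 6-month change yields a 0.42 effect size (ES")). The share of the variance in HbA1c change due to site, R, is not in the documents. I assume 1% to 10%.

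**1. Reproducing the plan's figure.** Normal approximation: n per arm = 2 × (1.96 + 0.842)² × (SD/difference)².
- 0.45% and SD 1.2: n = 112 per arm, power 80.1%. The noncentral t gives 79.8%. This reproduces the plan.
- 0.5% and SD 1.2: n = 91 per arm, and power at 112 is 87.7%. This does not reproduce the plan.

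I therefore use 0.45%. The stated effect size of 0.42 matches 0.5/1.2 = 0.417, whereas 0.45/1.2 = 0.375. That mismatch needs its own correction and does not affect this point.

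**2. Power gained by adding site.** If 1.2 already contains the between-site variance, the residual SD after adjustment is 1.2 × √(1 − R). Noncentral t, 112 per arm, 0.45%:

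| R (assumed) | Residual SD | Power with site | Gain over 79.8% |
|---|---|---|---|
| 1% | 1.194 | 80.2% | 0.4 points |
| 2% | 1.188 | 80.6% | 0.8 points |
| 5% | 1.170 | 81.8% | 2.0 points |
| 10% | 1.138 | 83.8% | 4.0 points |

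The standard error falls by about 0.5%, 1%, 2.5% and 5%. Five further site parameters reduce the degrees of freedom from 222 to 217, which changes power by less than 0.01 percentage points.

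If 1.2 is instead a within-site SD, the total SD in a model without site is 1.2/√(1 − R). Power is then 79.4%, 79.0%, 77.7% and 75.5% for the same four values of R.

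**3. Effect of chance site imbalance on the estimate.** Take six equal sites, N = 224, 112 per arm, unstratified allocation, and site effects with SD 1.2 × √R. The part of the arm difference due to site mix has

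SD = 1.2 × √R × √[(N² − N²/6)/(N − 1)]/112 = 1.2 × √R × 0.122.

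This is 0.015 HbA1c points at R = 1% and 0.046 at R = 10%. Simulating 20,000 allocations gave 0.0147 and 0.0463, with 95% of values within about 0.03 and 0.09. For comparison, the target is 0.45 and the standard error of the arm difference is 1.2 × √(2/112) = 0.160.

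**4. How often a site looks uneven.** With simple randomisation and six sites of 37, one site splits 23:14 or worse with probability 0.188. At least one of six does so with probability 1 − (1 − 0.188)⁶ = 0.71. This counts uneven-looking sites. Step 3 shows how little such unevenness moves the result.

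**The case against.** The strongest reply is that validity is not at stake. Patients are randomised individually. Under simple randomisation, omitting a prognostic factor leaves the estimate unbiased on average and the type I error at its nominal level, and chance imbalance is already reflected in the standard error. This stands, and it limits the point to precision.

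The allocation method is also undescribed. The primary analysis refers to a stratification variable in connection with caregiver status, and section 11 says that a formal protocol with detailed analytical methods is being developed. Site balancing is therefore not described, but not ruled out either. The model omission does not depend on this.

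Two stronger readings are tempting, and the documents do not support them.
- A reader might infer that the random draw of 400 patients from the list of 4,092 misses the added sites, because the enrolment table sets 4,092 beside 2 centres. But sections 5 and 6 give 4,092 as the count for the sites just listed, and sections 20 and 23 describe contacting randomly selected patients from the various study sites. What remains is a question about whether the figure was updated as sites were added.
- A reader might infer that the comparator is whatever care each site happens to give. Section 11 ties it to the 2018 ADA Standards, with routine visits every 3 months, monthly study-nurse calls and a checklist of adherence. Sites may still differ, but within a defined standard.

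Finally, stratifying six sites by caregiver status makes 12 strata for 224 patients, some possibly sparse. That is a fair caution about the remedy.

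**Conclusion.** The point holds as one of efficiency and consistency. The text names about six sites, the table says two, no site stratification is described, and the HbA1c models omit site. Adding site would raise power by about 0.4 to 4 points, and chance site imbalance has an SD of about 0.015 to 0.046 HbA1c points against a target of 0.45. Both ranges rest on an assumed site share of 1% to 10% of the variance in HbA1c change and on a difference of 0.45% with SD 1.2. The imbalance figures also assume six equal sites and unstratified allocation.

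A reader might take the 71% chance of an uneven site as a sign that the result is unreliable. It is not: it describes counts within sites and carries no implication of bias. The change is worth making because it is nearly free and because choosing the covariate in advance avoids a post hoc decision.

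**What to change.** 1. Add site as a fixed effect in the primary and secondary models, with a rule fixed before unblinded analysis for pooling small sites. Cost: about five degrees of freedom out of roughly 220.
2. Describe the randomisation method. If enrolment has not begun, also stratify the Biostatistics Unit's list by site, keeping the number of strata small given caregiver status (for example by pooling small sites first). If enrolment is under way, make the model change only.
3. Correct row 5 of the enrolment table to agree with sections 5 and 6, and say whether the two Queens practices count as one site.
4. Confirm in one sentence that the list of 4,092 patients covers every named site.

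Beyond the model term, the cost is a few edited sentences and, before enrolment, a new allocation list. No extra data collection is needed.
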